Study design	This open-label, non-interventional study (NIS) will prospectively collect UK specific data on the use of Afinitor in combination with exemestane in patients with metastatic or locally advanced ER+ breast cancer after progression on therapy with an NSAI in routine clinical practice. Dosage and scheduling of Afinitor in the treatment of these patients will follow the recommendations of the summary of product characteristics (SmPC) and the treating physician.
Population	Approximately two hundred postmenopausal women greater than 18 years of age with ER+ locally advanced or metastatic breast cancer for whom a decision has been taken to initiate treatment with Afinitor in combination with exemestane are eligible for this study. There are no exclusion criteria except the contraindications listed in the
	SmPC. Participating patients may not take part in any clinical study in

r

	parallel to this, as this does not constitute routine medical practice and is, therefore, counter to the aims of a NIS.
Variables	Primary Outcome Measures:
	The primary objective of this study is to describe two specific toxicities, namely stomatitis and NIP, in patients commencing treatment with Afinitor in combination with exemestane for ABC after progression on a NSAI. The descriptions will comprise incidence, severity, length of time to onset, duration, clinical course, specific management (prophylaxis and intervention) and will look to identify any potential predisposing factors on the likelihood of development.
	Secondary Outcome Measures:
	• to determine the dosing, schedule and duration of treatment with Afinitor and exemestane including any dose modifications/durations and reason(s); frequency of monitoring; prior and subsequent treatments and reason(s) for discontinuation.
	 to evaluate investigator-assessed progression-free survival (PFS) with Afinitor plus exemestane. Investigator-assessed disease progression may be based on clinical examination or radiographic or laboratory features, mirroring routine practice.
	 to capture changes in Quality of Life (QoL) scores over time and investigate the relationship between Health-Related Quality of Life (HRQoL), as measured by the EuroQol five-dimensional questionnaire (EQ-5D) and subjective well-being scores in ABC;

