9.1 Study design

This is an open-label, NIS of oral Afinitor (everolimus [RAD001]) in combination with exemestane in patients with metastatic or locally advanced ER+ breast cancer after progression on therapy with a NSAI. Afinitor (10mg daily) in combination with exemestane (25mg daily) will be prescribed in accordance with the SmPCs and supplied by pharmacy.

This is a NIS and, therefore, does not impose a therapy protocol, diagnostic/therapeutic procedure, or a visit schedule. Patients will be treated according to local prescribing information and routine medical practice in terms of visit frequency and types of assessments performed and only these data will be collected as part of the study.

The planned observation period per patient starts with initiation of treatment with Afinitor in combination with exemestane, but ends on completion of the observation phase. The observation phase completes once the last patient has been on study for 12 months. All antineoplastic therapies (surgery, medication, radiotherapy) for advanced breast cancer both

prior to initiation of Afinitor plus exemestane and post discontinuation should be recorded on the relevant eCRF pages. The treating physician will be asked to complete, if possible, at every patient visit the appropriate electronic case report form (eCRF). Below is the recommended assessment schedule that most likely mirrors the patterns of routine clinical care of most patients being treated with Afinitor (everolimus) in breast cancer. More frequent visits may be considered appropriate by the treating physician. Under these circumstances an appropriate eCRF should be completed for each visit. Data will be entered into an electronic data capture system allowing for continuous access to data and any potential reevaluations of the study design or conduct.

Time of data entry	At start of documentation	After approx. 2 weeks	Approx. Month 1	Approx. Months 3, and at 3- month intervals thereafter	At end of treatment
Obtain patient's written	х				
Informed consent*	N N				
Inclusion/exclusion criteria	X				
Demography	A Y				
Physical examination	X				
Vital signs	X				
ER, PoR status and Ki67	X				
Relevant medical history/current medical conditions	X				
Concomitant medications	Х				
Date of initial diagnosis	Х				
Date of metastatic relapse (if applicable) and sites involved	x				
Prior antineoplastic therapies (surgery, medication, radiotherapy) for advanced breast cancer	Х				
Prior history of stomatitis	Х				

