Thereafter, standard care would ideally be for patients to be contacted at 2 weeks, monthly then monthly to three monthly. The frequency of the visits will vary from patient to patient and due to clinician preference. Patients will be asked to complete the HrQoL and SWB questionnaires each time they attend the clinic. The HrQoL and SWB questionnaires will also be complete 30 days after trial end if possible as part of the end of trial visit.

9.3.2 **Primary outcome variable: stomatitis and non-infectious pneumonitis**

Instances of stomatitis and NIP will be assessed using the following variables:

- Incidence, severity, length of time to onset, duration and clinical course;
- Specific management of these events (including prophylaxis and interventions) will also be captured;

The expectation is that individuals participating in this study will be routinely questioned as to the presence of new or changed pulmonary symptoms consistent with lung toxicity. Computed Tomography scans and pulmonary function tests may be conducted, as clinically indicated, if there are symptoms that indicate that the patient has developed NIP. If NIP develops, the guidelines below should be followed. Table 9-2 provides dose modification instructions for stomatitis and NIP.

Table 9-2 Management of non-infectious pneumonitis and stomatitis

Adverse	Severity (Worst	Recommended	Management	Afinitor [®] Dose Adustment
Stomatitis	Grade 2 (symptomatic, but can eat and swallow modified diet)	Visual assessment	Symptomatic therapy only: mouthwashes, oral gels and sucralfate. Use water- based moisturizer to protect lips. Follow recommended oral care protocol.	Temporary dose reduction until recovery to ≤grade 1. Restart treatment at same dose. If stomatitis recurs at grade 2, interrupt dose until recovery to ≤grade 1. Restart treatment at 5mg daily.
	Grade 3 (symptomatic and unable to adequately eat or hydrate orally)	Visual assessment, including removal of dentures or partials	Symptomatic therapy only: mouthwashes, oral gels and sucralfate. Use water- based moisturizer to protect lips. Rinse mouth four times daily with a bland rinse such as salt and soda. Follow recommended oral care protocol	Temporary dose interruption until recovery to ≤grade 1. Restart treatment at 5mg daily.

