	Grade 4 (symptoms associated with life- threatening consequences)	Visual assessment, including removal of dentures or partials	Symptomatic therapy only: mouthwashes, oral gels and sucralfate. Use water- based moisturizer to protect lips. Rinse mouth four times daily with a bland rinse such as salt and soda. Follow recommended oral care protocol. Consider systemic therapy.	Discontinue treatment.
Non-infectious pneumonitis	Grade 2 (symptomatic, not interfering with ADL)	CT scan with lung windows. Consider pulmonary function testing including: spirometry, DL _{CO} and room air O ₂ saturation at rest. Repeat at least every 12 weeks until return to within normal limits. Consider a bronchoscopy with biopsy and/or BAL.	Symptomatic therapy only. Consider corticosteroids if symptoms are troublesome.	Reduce study treatment dose by one dose level until recovery to ≤grade 1. Study treatment may also be interrupted if symptoms are troublesome. Patients will discontinue study treatment if they fail to recover to ≤grade 1 within three weeks.
	Grade 3 (symptomatic, interfering with ADL; O ₂ indicated)	CT scan with lung windows and pulmonary function testing including: spirometry, DL_{CO} and room air O_2 saturation at rest. Repeat at least every six weeks until return to within normal limits. Bronchoscopy with biopsy and/or BAL is recommended, if possible.	Consider corticosteroids if infective origin is ruled out. Taper as medically indicated.	Hold treatment until recovery to ≤grade 1. May restart study treatment within three weeks at reduced dose (by one level) if evidence of clinical benefit.
	Grade 4 (life- threatening; ventilator support indicated)	CT scan with lung windows ad required pulmonary function testing, if possible, including: spirometry, DL _{co} and room air O ₂ saturation at rest. Repeat at least every six weeks until return to within normal limits. Bronchoscopy with biopsy and/or BAL is recommended, if possible.	Consider corticosteroids if infective origin is ruled out. Taper as medically indicated.	Discontinue treatment.

Novartis	Confidential	Page 29
Non-interventional study protocol		Afinitor [®] : BOUDICA

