9.3.3 Secondary Outcome Variables; Drug exposure

Everolimus (RAD001) dosing will commence as per current practice. Patients will be instructed to take everolimus (RAD001) orally with a large glass of water, once daily, at the same time each day with or without food. Patients will be instructed to take one tablet of 25mg exemestane orally as per the SmPC.

Confirmation of correct dosing with everolimus and exemestane will be recorded in the eCRF, with details of any interruptions in drug treatment or dosage alterations. Compliance will be assessed by the Investigator and/or study personnel at each visit using tablet counts and information provided by the patient or caregiver. This information should be included in the source document at each visit for both drugs (everolimus and exemestane).

The mean and median duration of exposure will be assessed. A record will also be maintained of any dose modifications with everolimus, including duration and reason(s).

Patients will continue to be treated at the discretion of the treating physician. Information on drug exposure will be collected on the Dosage Administration Record page of the eCRF.

After a patient's individual study involvement ends, routine clinical practice will continue under the direction of the Investigator.

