9.4 Data sources

Data sources will include patient medical records, including determination of the exposure to the study product and concomitant medication, as well as any adjustment in dosages. Additional sources will include laboratory reports and X-rays. The baseline characteristics, ECOG Performance Status and EQ-5D and SWB questionnaires may be entered directly into the electronic database during the study which will capture, check, store and analyse the data.

Novartis or an appropriate third party will initiate participating sites. Before study initiation, a Novartis representative (or their designee) will review the protocol and eCRF with the physicians and their staff.

Concomitant or prior medications entered into the database will be coded using the World Health Organisation (WHO) Drug Reference List. Medical History/Current Medical Conditions and AEs will be coded using the Medical Dictionary for Regulatory Activities (MedDRA) terminology.

Safety data will be available to Novartis throughout the study on the electronic database.

Data collection schedule

This is a NIS and does not impose a therapy protocol, diagnostic/therapeutic procedure, or a visit schedule. Patients will be treated according to the local prescribing information, and routine medical practice in terms of visit frequency and types of assessments performed and only these data will be collected as part of the study. The observation intervals will be in line with clinical routine e.g. after approximately two weeks, one and three months and thereafter at a three-month interval after the start of treatment with Afinitor and exemestane. The

treating physician will be asked to complete the appropriate eCRF at every patient visit, if possible.

For patients who discontinue prematurely, the reason for discontinuation should be determined.

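### Table 9-2 is worded as instructions to sites in a study that says it imposes no treatment or procedure, so management and dosing results for grade ≥2 events could partly reflect the protocol

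*Protocol*

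**What the plan says.** Section 9.1 states: "This is a NIS and, therefore, does not impose a therapy protocol, diagnostic/therapeutic procedure, or a visit schedule". Section 9.4, under the data collection schedule, repeats it: "This is a NIS and does not impose a therapy protocol, diagnostic/therapeutic procedure, or a visit schedule". The abstract says that Afinitor dosage and scheduling "will follow the recommendations of the summary of product characteristics (SmPC) and the treating physician", and Section 9.3.3 adds: "Patients will continue to be treated at the discretion of the treating physician".

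Section 9.3.2, on the primary outcome variable, reads: "If NIP develops, the guidelines below should be followed. Table 9-2 provides dose modification instructions for stomatitis and NIP". The first sentence concerns NIP only. The second presents the table as dosing instructions for both toxicities.

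Table 9-2 covers grades 2 to 4. Many entries leave room for judgement, but some do not:

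- Stomatitis grade 3: "Temporary dose interruption until recovery to ≤grade 1. Restart treatment at 5mg daily".
- NIP grade 2: "Patients will discontinue study treatment if they fail to recover to" grade 1 or lower within three weeks.
- NIP grade 2 testing: "Repeat at least every 12 weeks until return to within normal limits". For grades 3 and 4 the interval is at least every six weeks.
- Grade 4 of either toxicity: stop treatment.

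Specific management of the two toxicities is part of the primary objective (8.1). Dosage and schedule in routine practice, with reasons for reduction or discontinuation, is the key secondary objective (9.7.2). Frequency of monitoring is a further secondary objective (8.2).

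**The concern.** A descriptive study of routine care is informative only if the protocol does not tell sites what that care should be. Here the protocol both disclaims any influence on treatment and issues directions on dose, discontinuation and repeat testing for the two events of main interest. A site that follows the directions because they are in the protocol will produce results that look like UK practice but partly repeat Table 9-2.

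The results exposed are the interventions used, dose reductions and interruptions, restart doses, discontinuations and NIP monitoring frequency, all for grade ≥2 events. Incidence and stomatitis prophylaxis are not directly affected, and the table has no grade 1 row.

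**Working it through.** The plan gives no figure to reproduce on this point. The check is a comparison of texts, followed by a count for scale.

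**1. Do the texts conflict?** Sections 9.1 and 9.4 rule out an imposed therapy protocol or procedure. Section 9.3.2 directs that guidance be followed once NIP develops and describes the table's dose content as instructions. Both cannot hold unless the table is optional, and nothing in the protocol says that it is optional or that it merely restates the SmPC.

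**2. Does the rest of the protocol give the table force?**

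- Section 10 (regulatory and ethical compliance) has investigators sign that they will follow all instructions and procedures in the protocol. Section 9.3.2 uses the word instructions for this table.
- Section 9.8 has monitors check adherence to the protocol.
- Section 9.6 says that protocol deviations will be determined during the study.

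A site managing grade 2 NIP in its own way could reasonably expect a deviation to be recorded.

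**3. Which column binds?** The assessment column is headed as recommended. The dose-adjustment column carries no such qualifier, and the directive dose and discontinuation entries are in that column.

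**4. How many patients could fall under the table?** Inputs: about 200 patients (9.2), and BOLERO-2 rates in the Afinitor plus exemestane arm from Table 7-1 and Sections 7.2.1 and 7.2.2. Formula: expected number = 200 × proportion at grade ≥2.

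| Toxicity | Source | Proportion at grade ≥2 | Of 200 |
|---|---|---|---|
| NIP | Table 7-1, grades 2 + 3 + 4 | 6% + 3% + 0% = 9% | 18 |
| NIP | 7.2.2, cumulative risk at 48 weeks | 16% | 32 |
| Stomatitis | Table 7-1, grades 2 + 3 + 4 | 22% + 8% + 0% = 30% | 60 |
| Stomatitis | 7.2.1, cumulative risk at 48 weeks | 37% | 74 |

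The two toxicities should not be added, because one patient may have both. The counts assume that BOLERO-2 rates carry over to this study. Section 9.5 quotes higher all-grade NIP figures from UK audit data (36% and 39%), but these do not give a grade ≥2 rate.

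These are numbers of patients to whom the table could apply. They are not numbers whose care would change: that depends on how far sites would have departed from the table without it, which the protocol does not tell us.

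**The case against.** The best reply is that the protocol, read as a whole, leaves care with the physician. Besides the statements quoted above, Section 9.3.1 documents diagnostic measures only if done in routine practice. Section 9.3.2 itself says that CT and lung function tests are done when clinically indicated. Section 9.3.4.1, under tumour assessment, leaves management decisions with the local investigator. On this reading Table 9-2 is guidance loosely worded. That lowers the likely effect but does not remove the conflict. These are general statements, the direction in 9.3.2 is specific, and the protocol does not say which prevails. The CT sentence covers the work-up of suspected NIP; the direction that follows applies once NIP has developed.

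A second reply is that the consequence depends on the SmPC. If the table matches the label and UK sites already follow the label, little changes. This stands as a limit on size. Even so, a protocol instruction to follow label advice can raise adherence above what routine practice would show.

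A third reply is that stomatitis is a weaker case. This stands too: the direction to follow the guidance attaches to NIP, and the stomatitis management column lists generic symptomatic care that leaves variation to observe. A reader might also see a conflict with Section 7.2.1, which says that no definitive stomatitis treatment can be recommended. That passage concerns options for relief, so the conflict is slight.

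Three stronger inferences are tempting and not supported:

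- That the three-week rule would force grade 2 NIP patients off treatment, because Section 7.2.2 gives a median of 3.8 weeks to grade ≤1. That median is for grade 3 events; no grade 2 recovery time is given.
- That Section 7.2.2 shows sponsor guidance altering such results. It lists guideline implementation as a possible explanation for differing NIP incidence, not management.
- That the study's management results are already known to be distorted. The documents show a route for distortion, not its occurrence.

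**Conclusion.** The contradiction is real and clearest for NIP. Followed as written, Section 9.3.2 and Table 9-2 would steer the intervention, dosing, discontinuation and NIP monitoring results for grade ≥2 events that the study means to observe in routine practice.

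The size of the effect cannot be computed from the protocol and may be small. The table could apply to roughly 9% to 16% of patients for NIP and 30% to 37% for stomatitis, if BOLERO-2 rates hold. The conclusion rests on sites giving some weight to instructions that they have signed to follow, and on routine care differing in some respects from the table. The point should be corrected because it touches the primary and key secondary objectives and the correction is cheap.

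**What to change.** In Section 9.3.2, replace the two sentences that introduce Table 9-2 with a statement along these lines: Table 9-2 is reference information only; management, dosing and monitoring follow the SmPC and the treating physician; departures from the table are not protocol deviations. Change the NIP grade 2 discontinuation entry to advisory wording, for example that discontinuation may be considered if recovery to grade 1 or lower has not occurred within three weeks. The covering statement then governs the restart-dose and repeat-testing entries, so the other cells need not be rewritten. Matching individual cells to the SmPC would require the SmPC and is not proposed here.

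If patients have already been managed under the present wording, add to Section 9.9 that management and dosing results for grade ≥2 events may have been influenced by the protocol.

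The cost is a wording amendment, with no added visits, tests or data items. The downside is slightly less uniform guidance to sites; the SmPC and physician judgement still govern patient safety.

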9.7.2 Analysis of secondary objectives

The key secondary objective of this study is to report the Afinitor and exemestane dosage/schedule in routine clinical practice, including the duration of exposure and the main reasons for any dose reduction or discontinuation of Afinitor.

- Duration of Afinitor and exemestane treatment: Number of treatment days will be calculated as the difference between the date of the first dose and one day after the date of the last dose of the study. The actual duration of treatment will be calculated as the difference between the exposure period minus the number of days on which treatment was temporarily withdrawn.
- Main causes of dose reduction, dose escalation or withdrawal of Afinitor and exemestane will be captured

The analyses will be solely descriptive and comprise the description of the various items and the 95% CI.

Further technical details and discussions including imputation and details regarding missing data will appear in the statistical analysis plan, which will be finalised prior to database lock and the analysis.

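### In Table 9-2 the grade 2 stomatitis cell orders a dose reduction but then tells the physician to restart treatment, so the action and the return instruction do not describe the same event

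*Protocol*

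**What the plan says.** Section 9.3.2 introduces the table with "Table 9-2 provides dose modification instructions for stomatitis and NIP". The dose-adjustment column for grade 2 stomatitis begins "Temporary dose reduction until recovery to ≤grade 1. Restart treatment at same dose" and goes on, for a second episode, "If stomatitis recurs at grade 2, interrupt dose until recovery to ≤grade 1. Restart treatment at 5mg daily". The grade 3 stomatitis row reads "Temporary dose interruption until recovery to ≤grade 1. Restart treatment at 5mg daily".

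For pneumonitis, the grade 2 row reads "Reduce study treatment dose by one dose level until recovery to ≤grade 1. Study treatment may also be interrupted if symptoms are troublesome", and the grade 3 row begins "Hold treatment until recovery to ≤grade 1. May restart study treatment within three weeks at reduced dose".

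Three other parts of the protocol bear on how much weight the cell carries:
- Section 9.1 states that the study "does not impose a therapy protocol, diagnostic/therapeutic procedure, or a visit schedule".
- Table 9-1 and Section 9.3.3 set out what is recorded about dosing.
- Section 9.7.2 defines actual treatment duration as the "exposure period minus the number of days on which treatment was temporarily withdrawn".

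**The concern.** The first sentence of the cell describes a reduction, during which the drug is still taken. The second describes a restart, which makes sense only if the drug was stopped. A reader who gives weight to the first sentence lowers the dose. A reader who gives weight to the second stops the drug until recovery. Nothing else in the protocol says which is meant.

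Two things are at stake. First, this is a conflicting dosing instruction for a common toxicity, in a table presented to sites as instructions. Second, the primary objective includes describing how stomatitis is managed in routine UK practice. If sites consult the table and read it differently, some of the variation in management that the study reports could come from the protocol's wording and not from clinical practice. The frequencies of reductions and pauses, which belong to the key secondary objective in Section 9.7.2, would show that variation too.

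**Working it through.** The protocol gives no figure to reproduce on this point. The check is a comparison of the rows of Table 9-2, followed by one calculation for scale.

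**Step 1: action and return instruction, row by row**

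| Row of Table 9-2 | Action ordered | Restart wording? | Do they match? |
|---|---|---|---|
| Stomatitis grade 2, first episode | Reduction | Yes, at the same dose | No |
| Stomatitis grade 2, recurrence | Interruption | Yes, at a stated dose | Yes |
| Stomatitis grade 3 | Interruption | Yes, at a stated dose | Yes |
| Pneumonitis grade 2 | Reduction, with interruption as a separate option | No | Yes |
| Pneumonitis grade 3 | Hold | Yes, at a reduced dose | Yes |

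The grade 4 rows order discontinuation and raise no question of return. The table otherwise treats reducing and stopping as different actions and keeps restart for the second. The first-episode cell for grade 2 stomatitis is the only one that mixes them.

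**Step 2: what the two readings share and where they part**

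The change is described as temporary and as lasting until recovery. The same cell then gives a different return dose for a recurrence. Taken together, the wording points to the dose before the episode as the meaning of the same dose, whichever reading is taken. The readings therefore part mainly over what the patient takes during the episode: a lower dose or nothing.

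**Step 3: whether the data depend on the reading**

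- Table 9-1 lists dose reductions and pauses in treatment as separate items, together with the reason for adjustment.
- Section 9.3.3 asks for details of interruptions and dose changes, for the duration and reason of everolimus modifications, and for tablet counts at each visit.
- Section 9.7.2 subtracts days on which treatment was actually withdrawn.

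Exposure is thus derived from what the patient took, not from Table 9-2. A site that reduces records a reduction, and a site that stops records a pause. The derivation handles each correctly.

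**Step 4: scale**

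Table 7-1 gives stomatitis in the Afinitor plus exemestane arm of the earlier phase III study as 29% grade 1, 22% grade 2, 8% grade 3 and 0% grade 4. These add up to the all-grade figure: 29 + 22 + 8 + 0 = 59%. The grade columns therefore do not overlap. Applying the grade 2 share to the planned sample:

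0.22 × 200 = 44 patients.

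This assumes that the earlier rate carries over. Section 8 says that UK audit data suggest a higher incidence of adverse events than that study reported, so the number could be larger. It counts patients who could meet the row, not patients whose treatment or data would change.

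**The case against.** The strongest answer is that the table has little force. The study imposes no therapy, Section 9.3.3 leaves treatment to the physician's discretion, and Section 7.2.1 says that no definitive recommendation for treating stomatitis can be given. In Section 9.3.2 the sentence saying that the guidelines should be followed is tied to the development of pneumonitis, not stomatitis. A lenient reader may also take the cell to mean a temporary reduction followed by a return to the earlier dose. These arguments lower the weight of the point but do not remove it. The protocol still calls the table dose modification instructions, and the lenient reading has to overlook the way the table uses restart everywhere else.

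A reader might infer more than the protocol supports in three ways:

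- **That the exposure results are wrong, or that one episode is counted in two ways.** Step 3 rules this out on the text. A physician influenced by the wording would produce a real difference in treatment, and the planned data collection is set up to capture it.
- **That the duration of treatment is affected in each of about 44 patients.** That would require every such patient to be managed by this cell and the record not to show what was done. The protocol gives no length for grade 2 episodes, so no effect on duration can be derived.
- **That the eCRF must be changed to separate reductions from interruptions.** The protocol already requires this.

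**Conclusion.** The point holds as an internal contradiction in one operative table cell. The action ordered for a first grade 2 stomatitis episode is a reduction, the return instruction presupposes a stop, and no other part of the protocol resolves the conflict. The consequence is a risk of inconsistent management of a primary toxicity whose management the study is meant to describe. It is not a demonstrated error in recorded exposure.

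About 44 of 200 patients could meet the row if the Table 7-1 rate applied. How many would be managed differently because of the wording, and by how much treatment duration would differ, cannot be determined from the protocol. The non-interventional design limits the seriousness. The correction is still worth making, because the cell concerns dosing and costs almost nothing to put right.

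**What to change.** The sponsor's clinical authors should reconcile the two sentences of the first-episode grade 2 stomatitis instruction with each other, with the other rows of Table 9-2, and with the product information that Sections 4 and 9.1 rely on. After the change, the action and the return instruction should describe the same event, and the dose to which the patient returns should be named without ambiguity. Which action or dose is right is for those authors to settle and is not proposed here.

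The cost is one table cell in a protocol amendment and a notice to sites. Data collection and the exposure derivation can stay as they are.
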